EUS-guided tissue acquisition of pancreatic masses is the main modality for the diagnosis of pancreatic solid tumors including adenocarcinoma and neuroendocrine tumor. Traditionally, this is done through sampling with fine needle aspiration (FNA); however, this approach has led to variable diagnostic yield with approximately 20% of the samples being non-diagnostic¹⁻³ needing repeat procedures. Several tertiary centers worldwide have adopted rapid on-site evaluation (ROSE) of cytopathology, where a cytopathologist is at the bedside of the procedure and looking at each samples in real-time to give feedback to the endoscopists in terms of adequacy and preliminary diagnosis of their EUS-guided FNA. ROSE has been shown to increase the diagnostic yield by 10 to 15%¹ ⁴. Although currently unavailable at most Canadian sites, hospitals have been contemplating the implementation of ROSE in hopes of improving care for patients with pancreatic cancer and to prevent the need for repeat procedures and its associated costs and potential adverse events. Recently, however, novel core biopsy needles have been developed for fine needle biopsy (FNB) and histological assessment⁵. These needles allow for the acquisition of core samples with intact tissue architecture enabling immunohistochemical staining thereby enhancing the diagnostic yield. Although some studies suggest that FNB alone may be just as effective as FNA with ROSE, there are no comparative outcomes trials. As such, the goal of our study is to compare EUS-FNB with core needle sampling alone vs. EUS-FNA with ROSE in pancreatic solid lesions. If shown to be equivalent, FNB could potentially obviate the need for ROSE and be implemented in a more readily and affordable fashion across Canada.

Objectives:

Aim: To compare the diagnostic accuracy of EUS-FNB alone vs. EUS-FNA with ROSE in patients with solid pancreatic masses suspected to be of malignant origin.

Hypothesis: EUS-FNB is non-inferior to EUS-FNA with ROSE in the diagnostic accuracy for solid pancreatic masses while being associated with fewer needle passes and shorter procedure time.

Primary outcomes

- Diagnostic accuracy defined as (true positive + true negative)/all samples
- Final diagnosis will be based on the following criteria
- A) Final diagnosis of malignancy (one of the following):
 - histological evidence of malignancy on the corresponding subsequent surgical specimen
 - presence of an unresectable lesion during subsequent surgery
 - malignant cytology/pathology on EUS-sampling followed by documented locoregional progression/development of metastases on follow-up axial imaging.
- B) Final diagnosis of benign pancreatic mass (one of the following):
 - surgical pathology or exploration showing the absence of malignancy

- follow-up imaging at > 6 months reporting stability of the pancreatic lesion
- cytological or histopathological diagnosis of benign disease with an appropriate clinical course of disease for minimum of 6 months

Secondary Outcomes

- Diagnostic characteristics: sensitivity, specificity, positive and negative predictive value
- Specimen adequacy: defined as the proportion of samples in which a final histopathological diagnosis could be made
- Median number of needle passes, procedural time
- Rate of procedure-related adverse events with severity graded as per the ASGE lexicon⁶
- Cost-effectiveness

Methods:

EUS procedure:

Procedures are performed with a linear echoendoscope under conscious sedation. EUS-FNB is performed with a 22 gauge Core-needle. Tissue sampling technique is standardized between the endoscopists. Two passes are performed using the core needle. The biopsied samples are then expressed using a stylet into a jar filled with 10% formalin. A third pass is allowed if, on macroscopic inspection of the acquired sample, the specimen is deemed insufficient by the endoscopist. EUS-FNA with ROSE is performed with a 22 gauge FNA needle. The sampled specimen is expressed into a glass slide with a stylet; then using another glass slide the sample is spread out to make smears on two slides. Each pair of slides is then numbered according to their respective needle passes. One slide is air dried and stained with modified Giemsa stain for ROSE, while the other slide is fixed in 95% ethanol and later coated with with Pananicolaou stain.

This is a multi-center, randomized, single blinded, non-inferiority, trial comparing EUS-FNB alone to EUS-FNA with ROSE in the diagnosis of solid pancreatic masses. Following consent, patients are randomized, at the time of the procedure, to undergo either EUS-FNB alone or EUS-FNA with ROSE. The randomization sequence will be generated by a computerized randomization scheme using a block size of 10 stratified according to the endoscopist.

Inclusion Criteria:

- 1. Age > 18 years
- 2. Patients referred for EUS evaluation of a definite solid pancreatic mass noted on CT/MRI/EUS, in which malignancy is suspected with no previous histological diagnosis

Exclusion Criteria: 1.

- 1. Age < 18 years, pregnant patients
- 2. Uncorrectable coagulopathy PT>50% of control, PTT>50 sec, or INR>1.5 and/or uncorrectable thrombocytopenia platelet count<50, 000109/L.

Feasibility: The primary analysis is a noninferiority comparison of EUS-FNB vs. EUS-FNA with ROSE in terms of diagnostic accuracy, which, according to the most recent literature, is approximately 90% for both modalities. The margin of noninferiority is set at 10% in accordance with the USFDA recommendations. To achieve a statistical power of 80% with a two-sided type I error of 5%, a total of 224 patients (112 per group) is needed. Assuming a 5% dropout rate, a final sample size of 236 (118 per group) is estimated. The study is anticipated to take 2 years to complete.

Analysis: An intention-to-treat analysis will be carried out. The noninferiority hypothesis for the primary outcome will be assessed using the Z-test with a 95% two-sided confidence interval of the difference in the diagnostic accuracy and the margin of noninferiority. Interim analysis is planned after 50% of the cohort is recruited. If a > 20% difference in sensitivity is found between both methods then the study will be terminated early. Exploratory imaging and patient predictors of a diagnostic sampling is carried out using standard multivariable logistic regression analysis.

Cost-effectiveness:

A decision tree will be created for the two possible sampling approaches. Probability assumptions will be extracted from the RCT. Costs will be determined from the RAMQ. Third-party costs related to the procedure and downstream management costs will be determined based on the RCT resource utilization data. Deterministic and probabilistic sensitivity analyses will be undertaken.

Patient follow-up:

Patients will be contacted by telephone interview at 48-72 hours post procedure to ensure that no adverse events have occurred. All other follow-up will be standard of care and at the discretion of the treating physician.

Anticipated results:

We anticipate that the results will show that EUS-FNB alone will be non-inferior to EUS-FNA with ROSE in the diagnostic accuracy of solid pancreatic masses. We also expect that both modalities will have similar diagnostic characteristics such as sensitivity, specificity, and positive and negative predictive value. Finally, the use of EUS-FNB will likely be associated with fewer needle passes, shorter procedure time, and be more cost-effective.

If our data is consistent with the anticipated results then it would have a large impact on improving diagnostic yield of EUS tissue acquisition in pancreatic mass and potentially obviate the need for on-site cytopathology at a time where centers across Canada are contemplating the addition of this effective but expensive and resource intensive modality.

MULTICENTER GUIDELINES

Protocol Chair

The Protocol Chair is responsible for performing the following tasks:

- Coordinating, developing, submitting, and obtaining approval for the protocol as well as its subsequent amendments
- Assuring that all participating institutions are using the correct version of the protocol.
- Taking responsibility for the overall conduct of the study at all participating institutions and for monitoring the progress of the study.
- Reviewing and ensuring reporting of Serious Adverse Events (SAE)
- Reviewing data from all sites

Coordinating Center

The Coordinating Center is responsible for performing the following tasks:

- Ensuring that REB approval has been obtained at each participating site prior to the first patient registration at that site, and maintaining copies of REB approvals from each site.
- Managing central patient registration.
- Collecting and compiling data from each site.
- Establishing procedures for documentation, reporting, and submitting of AE's and SAE's to the Protocol Chair, and all applicable parties.
- Facilitating audits by securing selected source documents and research records from participating sites for audit, or by auditing at participating sites.

Participating Sites

Participating sites are responsible for performing the following tasks:

- Following the protocol as written
- Submitting data to the Coordinating Center.
- Providing sufficient experienced clinical and administrative staff and adequate facilities and equipment to conduct a collaborative trial according to the protocol.
- Maintaining regulatory binders on site and providing copies of all required documents to the Coordinating Center.
- Collecting and submitting data according to the schedule specified by the protocol.

ANTICIPATED RISKS

We do not anticipate major risk or discomfort beyond that associated with the conventional procedure. Both EUS-FNA with ROSE and FNB alone are part of standard or care. The following are conventional risks associated with EUS-FNA or FNB.

- 1) Perforation: Only physicians specially trained in EUS will be performing these procedures. The exact risk is minimal (<1%).
- 2) Infection: It is not standard practice to give antibiotics to all patients prophylactically for either percutaneous liver biopsy or EUS-FNA of noncystic lesions. Therefore, no subjects will receive antibiotics prophylactically for EUS sampling except those patients at risk for infective endocarditis according to American Heart Association guidelines.
- 3) Bleeding: The exact risk is minimal (1 in 5,000 chance). Doppler examination will be performed under EUS guidance prior to biopsy to ensure that the needle does not traverse a blood vessel. As a precautionary measure,

furthermore, all patients will have PTT, PT/INR, hemoglobin, and platelet count checked prior to the procedure. Those below acceptable standards will not be offered inclusion into the study. Frequent vital signs will be measured and recorded. If vital signs are abnormal and prolonged, a repeat CBC and possibly CT scan will be performed after procedure to ensure the absence of internal or external hemorrhage. These measures should ensure any clinically significant hemorrhage is detected and treated in a timely manner.

- 4) Pancreatitis (risk: 1%): Will be detected by the presence of pain with or without nausea and vomiting after pancreatic biopsy. If present, the patient will be hospitalized, kept NPO, and receive IV hydration.
- a. Steps taken to minimize the risks.
 Adherence to the standard of practice of EUS-guided tissue sampling at the McGill University Health Center as outlined above
- b. Financial risks to the participants. None.

ADVERSE EVENT REPORTING

Definition of Adverse Event (AE)

An adverse event is the development of an undesirable medical condition or the deterioration of a pre-existing medical condition following or during exposure to a procedure done, whether or not considered causally related to the procedure. An undesirable medical condition can be symptoms (e.g., nausea, chest pain), signs (e.g., tachycardia, enlarged liver) or the abnormal results of an investigation (e.g., laboratory findings, electrocardiogram).

Definition of Serious Adverse Event (SAE)

A serious adverse event is an AE occurring during the procedure or any time after the procedure, that fulfills one or more of the following criteria:

- Results in death
- Is immediately life-threatening
- Requires in-patient hospitalization or prolongation of existing hospitalization
- Results in persistent or significant disability or incapacity
- Is a congenital abnormality or birth defect
- Is an important medical event that may jeopardize the patient or may require medical intervention to prevent one of the outcomes listed above

Coordinating Center

The Coordinating Center is the central location for the collection and maintenance of documentation of adverse events and is responsible for submitting adverse event reports to the REB promptly. The Coordinating Center will maintain documentation of all adverse event reports for each participating site. Adverse event reports submitted to the Coordinating Center must be signed and dated by

the participating site's Principal Investigator. The Coordinating Center will provide appropriate forms to be used by all participating sites for reporting adverse events. Information to be provided must include:

- Subject ID number, and initials
- Date of the event
- Description of the event
- Description of site's response to the event
- Assessment of the subject's condition
- Subject's status on the study (on study, off study, etc.)

Participating Sites

Participating sites are responsible for reporting adverse events to their REB according to its specific requirements and to the Coordinating Center as follows: Fatal Events whether anticipated or unanticipated, and whether or not related to the study must be reported to the Coordinating Center within 24 hours of the participating site Principal Investigator's learning of the event.

Serious and Unanticipated Adverse Events must be reported to the Coordinating Center within 24 hours of the participating site Principal Investigator's learning of the event.

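### The benign criterion of stability at more than 6 months has no tissue condition, so a malignant sample from an unoperated, stable lesion is scored as a false positive

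*Protocol*

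**What the plan says.** The primary outcome is "Diagnostic accuracy defined as (true positive + true negative)/all samples" (Protocol, Primary outcomes). True and false are judged against a final diagnosis built from two lists, and one item of a list is enough.

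- **Malignant:** malignant histology at later surgery; an unresectable lesion found at later surgery; or "malignant cytology/pathology on EUS-sampling followed by documented locoregional progression/development of metastases on follow-up axial imaging".
- **Benign:** surgery or exploration showing no malignancy; "follow-up imaging at > 6 months reporting stability of the pancreatic lesion"; or "cytological or histopathological diagnosis of benign disease with an appropriate clinical course of disease for minimum of 6 months".

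No order of precedence between the lists is given. Secondary outcomes include "Diagnostic characteristics: sensitivity, specificity, positive and negative predictive value". The population has "a definite solid pancreatic mass noted on CT/MRI/EUS, in which malignancy is suspected with no previous histological diagnosis" (Inclusion Criteria). Feasibility plans on the comparison "in terms of diagnostic accuracy, which, according to the most recent literature, is approximately 90% for both modalities". After one telephone call at 48 to 72 hours, follow-up is left to routine care (Patient follow-up).

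**The concern.** The third benign criterion requires benign tissue; the second says nothing about tissue. Take an unoperated patient whose sample shows malignancy and whose lesion is stable beyond 6 months. No malignant criterion is met, because there was neither surgery nor progression, and the stability criterion is met. The final diagnosis is benign and the malignant sample is an error. Nothing sets aside lesions that are stable because they grow slowly or are under treatment, and the background section names neuroendocrine tumor among the lesions to be diagnosed. If the lesion is stable at first and progresses later, the patient meets both lists and nothing says which prevails.

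This alters the primary outcome directly. It lowers measured accuracy, specificity and positive predictive value, and it shrinks any true difference between the arms, which matters in a non-inferiority trial.

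A secondary point concerns the malignant list. Its only route without surgery requires a malignant EUS sample. An unoperated missed cancer that progresses, with no malignant repeat EUS sample, meets neither list and has no final diagnosis.

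**Working it through.** **The criteria applied to an unoperated patient**

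| EUS sample | Course | Malignant list | Benign list | Result |
|---|---|---|---|---|
| malignant | progression | met | not met | true positive |
| malignant | stable > 6 months | not met | met | false positive |
| malignant | stable, then progression | met | met | undetermined |
| benign | stable > 6 months | not met | met | true negative |
| benign or non-diagnostic | progression | not met | not met | no final diagnosis |

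**Inputs.** From Feasibility and Analysis: accuracy 90% in both arms, margin 10 points, 112 per arm, two-sided 95% interval. Assumed, because the protocol gives no figure: 80% malignant, specificity 100%, and the shares td and tm of detected and missed cancers that are unoperated and stable, taken as the same in both arms. Accuracy of 90% then means sensitivity s = 0.875, and 80% means s = 0.75.

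**The plan's own sample size.** n = (z_alpha + z_0.80)² × 2 × 0.9 × 0.1 / 0.1². With z_alpha = 1.96, n = 142 per arm; with 1.645, n = 112. So 112 matches a one-sided 5% test, and at the stated two-sided 5% the power with 112 is about 70%. That is a separate matter; 70% is used here only as the starting point.

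**Formulas.** Accuracy = 0.2 + 0.8[s(1 − td) + (1 − s)tm]. Measured gap = true gap × (1 − td − tm). Chance of declaring non-inferiority = Phi((0.10 − gap)/SE − 1.96), with SE² = [p1(1 − p1) + p2(1 − p2)]/112.

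*Case 1: only detected cancers affected (tm = 0).* At td = 0.2 the accuracies are 0.2 + 0.8 × 0.875 × 0.8 = 0.76 and 0.2 + 0.8 × 0.75 × 0.8 = 0.68. SE = √[(0.1824 + 0.2176)/112] = 0.0598, and Phi(0.02/0.0598 − 1.96) = 0.052.

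| td | Accuracy, better arm | True 10-point gap reads | False non-inferiority |
|---|---|---|---|
| 0 | 90% | 10 | 2.5% |
| 5% | 86.5% | 9.5 | 3.1% |
| 10% | 83% | 9 | 3.8% |
| 20% | 76% | 8 | 5.2% |

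Per 100 patients there are 70 detected cancers, 10 missed and 20 benign lesions. Specificity = 20/(20 + 70td), which reads 85, 74 and 59%. Positive predictive value = 1 − td, which reads 95, 90 and 80%. Both are truly 100%.

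*Case 2: the same share of missed cancers is also stable (td = tm).* A tissue condition recodes detected cancers only, so after the fix td = 0 and tm stays.

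| Share | As written | After the fix |
|---|---|---|
| 5% | 3.9% | 3.2% |
| 10% | 5.7% | 4.1% |
| 20% | 10.3% | 6.7% |

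The fix removes about half of the excess over 2.5%. The rest comes from stable missed cancers counted as true negatives.

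*Case 3: arms truly equal, td = tm.* The measured difference stays at zero, but accuracy reads 87, 84 and 78% and the variance rises. At 20%, SE = √(2 × 0.78 × 0.22/112) = 0.0554 and power = Phi(0.10/0.0554 − 1.96) = 44%. At 5, 10 and 20%, power is 60, 53 and 44%, against about 70%.

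**Secondary point.** A missed cancer adds nothing to the accuracy numerator whether it is a false negative or unclassified, and it stays in the denominator, so accuracy does not change. Let u be the share of detected cancers without a malignant final diagnosis and v the share of missed cancers with one. Measured sensitivity = s(1 − u)/[s(1 − u) + (1 − s)v]. A true 87.5% reads 92.1% at u = 0, v = 0.6, and 87.5% at u = 0.4, v = 0.6, where the losses are equal. A true gap of 90% against 65% reads 18.2 points in the first case and 25.0 in the second.

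**The case against.** Four arguments weigh on the other side.

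- **Size.** The protocol gives no share of detected cancers that stay unoperated and stable, and the effect is small if that share is small. This stands. The coding error follows from the text, but its size does not.
- **Attribution.** A reader might charge all of the 10.3% in Case 2 to the missing tissue condition. The documents do not support that: 6.7% remains after the repair, because a stable missed cancer has no malignant tissue. Case 2 may also set tm too high, since a non-diagnostic sample is not plainly a true negative. Case 1 is the cleaner measure.
- **Direction.** A reader might infer that the trial is biased towards non-inferiority. That holds only if a true gap exists. Under the protocol's own assumption of equal accuracy, the defect makes non-inferiority harder to show.
- **Unclassified missed cancers.** A reader might infer that these inflate the primary outcome. They do not while all samples form the denominator. The malignant criterion does not say index sample, so a malignant repeat sample followed by progression would qualify. Sensitivity, and with it the interim rule "If a > 20% difference in sensitivity is found between both methods then the study will be terminated early", is distorted only if missed cancers lose their final diagnosis more often than detected ones.

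It can also be said that an unseen statistical analysis plan may settle precedence and unclassifiable patients. That is fair for those two items. It does not answer the main point, since an analysis plan could not reclassify a patient who meets a stated benign criterion without contradicting the protocol.

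**Conclusion.** The point holds as a wording fault in the reference standard of the primary outcome. Read as written, a malignant sample from an unoperated lesion stable beyond 6 months is a false positive. With 5 to 20% of detected cancers affected and no missed cancer recoded, measured accuracy falls from 90% to between 86.5 and 76%, and false non-inferiority at the margin rises from 2.5% to between 3.1 and 5.2%. If the arms are equal, the cost is power instead. These figures rest on 80% malignancy, 100% specificity and equal shares in both arms, none of which the protocol states.

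The gap in the malignant list is real but secondary: it leaves accuracy unchanged, and its effect on sensitivity depends on shares that are not given. The criteria should be corrected. The documents do not show an effect large enough to say that the primary conclusion is bound to be wrong.

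**What to change.** 1. Limit the stability criterion to patients with no malignant tissue diagnosis.
2. In the primary analysis, count an unoperated patient with a malignant sample and a stable lesion as malignant. Repeat the primary result with these patients counted as not confirmed, that is, not correct.
3. Let documented progression, metastases, death from the cancer or later malignant tissue establish malignancy whatever the index sample showed.
4. State the precedence: surgical findings first (pathology, unresectable lesion, exploration); then later tissue, progression, metastases or cancer death; then the tissue result together with stability or a benign course.

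This is a protocol wording change with no added imaging or visits, but it has three costs. Accepting unconfirmed malignant samples favours specificity and positive predictive value; the repeat analysis shows by how much the primary result depends on that choice. Cancer deaths and tissue obtained elsewhere must be sought in records, because only the 48 to 72 hour call is scheduled. Missed cancers that stay stable remain misclassified.

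### Specimen adequacy counts only histopathological diagnoses, while the only FNA handling described is cytology smears, so the definition read literally favours FNB

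*Protocol*

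**What the plan says.** Under Secondary Outcomes the protocol lists specimen adequacy, "defined as the proportion of samples in which a final histopathological diagnosis could be made".

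Methods (EUS procedure) sends the two arms' material down different routes. For FNB: "The biopsied samples are then expressed using a stylet into a jar filled with 10% formalin". For FNA with ROSE: "then using another glass slide the sample is spread out to make smears on two slides". The two slides are then treated as follows: "One slide is air dried and stained with modified Giemsa stain for ROSE, while the other slide is fixed in 95% ethanol", the second slide being stained later with a Papanicolaou-type stain. No formalin specimen, cell block or other histology preparation is described for FNA.

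The benign final-diagnosis criterion under Primary outcomes accepts a "cytological or histopathological diagnosis of benign disease" with a compatible clinical course. The malignant criterion likewise accepts either cytology or pathology from EUS sampling.

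**The concern.** The two arms produce different kinds of specimen, and the adequacy rule names the kind that only one arm is described as producing. A smear read by a cytopathologist can give a firm diagnosis, but it is a cytological one. If the rule is applied as worded, such a sample counts as a failure in the FNA arm, while an equally informative core counts as a success in the FNB arm. Part or all of any observed difference would then come from the definition and not from the needles.

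The trial asks whether FNB alone can replace FNA with on-site cytopathology, so readers will look at adequacy directly after accuracy. It is also a multi-centre trial whose sites are told to follow the protocol as written. One site may count diagnostic cytology and another may not, and the result would then depend partly on local interpretation.

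**Working it through.** The protocol states no expected adequacy rate, so there is no figure to reproduce. The check is a comparison of texts, followed by an illustration of size.

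**Texts side by side**

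1. Outcome rule (Secondary Outcomes): a final histopathological diagnosis is required.
2. FNB specimen (Methods): formalin, so histology is available.
3. FNA specimen (Methods): smears on two slides, one Giemsa-stained for ROSE and one ethanol-fixed for a Papanicolaou-type stain. Both are cytology preparations.
4. Background: ROSE is described as cytopathology read by a cytopathologist, and histological assessment is attributed to the core needles.
5. Final-diagnosis criteria (Primary outcomes): cytology and histopathology are named as alternatives, and both are accepted.

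Items 2 to 4 place histology in the FNB arm only. Item 5 shows that the protocol names both terms where both are meant. Item 1 names one.

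**Illustration of size**

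Let *f* be the true proportion of samples that give a diagnosis of either kind, assumed equal in both arms. Let *s* be the share of diagnostic FNA samples that also yield a histopathological diagnosis. Assume that every diagnostic FNB sample does. Then:

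- counted FNB adequacy = *f*
- counted FNA adequacy = *f* × *s*
- spurious difference = *f* − *f* × *s* = *f*(1 − *s*)

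The protocol fixes neither *f* nor *s*; both are assumptions. For orientation on *f*, the background puts non-diagnostic FNA at about 20%, so the yield is about 80%, and says ROSE raises yield by 10 to 15%. Read as absolute points, that gives 80 + 10 = 90% to 80 + 15 = 95%. Read as a relative gain, it gives 80 × 1.10 = 88% to 80 × 1.15 = 92%. These are diagnostic-yield figures, not stated adequacy rates. The range 80 to 95% covers both readings.

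| *f* | *s* = 0 | *s* = 0.25 | *s* = 0.50 | *s* = 1 |
|---|---|---|---|---|
| 0.80 | 80 points | 60 points | 40 points | 0 |
| 0.90 | 90 points | 67.5 points | 45 points | 0 |
| 0.95 | 95 points | 71.25 points | 47.5 points | 0 |

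For example, *f* = 0.90 and *s* = 0.25 give 90% against 0.90 × 0.25 = 22.5%, a difference of 67.5 points. With the protocol's 112 patients per group, taken as one sample each, and a two-sided 5% test, power to declare a difference exceeds 99.9% in every cell with *s* of 0.50 or less. The smallest such gap is 80% against 40%. If the rule counted cytology as well, equal true yields would give a difference of 0 whatever *s* is.

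**The case against.** The strongest reply is that the word was meant loosely, to cover any final diagnosis issued by the pathology laboratory. The background supports this: it speaks of ROSE giving feedback on the adequacy of FNA samples, which makes no sense if cytology can never be adequate. The terminology also varies elsewhere. The inclusion criterion excludes patients with an earlier histological diagnosis, and a strict reading of that would admit someone whose earlier cytology was already malignant, which is unlikely to be intended. This part of the objection stands: the looser meaning is plausible. It does not remove the defect, because the paired wording in the final-diagnosis criteria points the other way and a stated outcome definition should not turn on the reader.

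A second reply is that smear-only handling is an inference. The protocol does not say that no cell block or other preparation is made from FNA material. That also stands, and it is why the bias is given as a range in *s*. A reader might infer that the outcome is wholly decided by arm, with 0% adequacy for FNA. The documents support that only if the literal reading applies and no histology preparation is ever made.

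A reader might also infer that the cost-effectiveness analysis is distorted. The Cost-effectiveness section says that probabilities come from the trial, but it does not name adequacy as one of them, so the document does not establish that consequence.

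Finally, a statistical analysis plan that is not shown might set out the scoring. The protocol does not leave the matter open, however. It states a definition, and that definition is what needs correcting.

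**Conclusion.** Wrong as written, and confined to one secondary outcome. Applied literally, the definition does not count FNA samples that have a diagnostic cytology result, and so it biases the adequacy comparison towards FNB. For an assumed common yield of 80 to 95%, the artefact runs from 0, if all diagnostic FNA samples also yield histology, up to the whole of that yield, if none do. The upper end is a bound under the literal reading, not a prediction of what the trial will report. The power figures show only that a gap of 40 points or more would be declared significant. They are no evidence that *s* is in fact 0.50 or less.

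The primary outcome does not share the fault, because its final-diagnosis criteria accept cytology. The non-inferiority conclusion on diagnostic accuracy is therefore untouched by this point. The change should be made because it is cheap and the bias has a known direction.

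**What to change.** Redefine specimen adequacy as the proportion of samples in which a final cytological or histopathological diagnosis could be made from the study EUS sampling, with the same rule in both arms.

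In the same sentence, state the counting unit (patient or needle pass) and use it in both arms. This is a smaller, separate clarification: FNA slides are numbered by pass, while FNB material is placed in a jar with no labelling by pass described, so a count of samples could mean different things in the two arms.

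If the yield of histological cores is of interest, report it separately under its own name and not as adequacy.

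The cost is one sentence of protocol wording. No procedure, visit or sample size changes.
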